#### Comparison A:

Hypothesis: The proportion of women with treatment failure on tenofovir containing antiretroviral treatment is different than that in women on tenofovir-sparing antiretroviral treatment.

This includes study population 1 and 3, i.e. only women who were in the tenofovir gel arm of a trial at the time they acquired HIV infection. The proportion of treatment failures in women on a tenofovir containing regimen will be compared to the proportion of treatment failures in women on a tenofovir-sparing regimen.

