## **2. Study Objectives**

### **2.1 Primary Objective:**

To determine whether prophylactic exposure to tenofovir gel at the time of infection alters the subsequent therapeutic response to a tenofovir containing antiretroviral regimen

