## **7. Study Intervention:**

Antiretroviral therapy will be initiated when any one of the following criteria are met:

- reach a CD4+ count of less than 350 cell/mm^3
- acquire an AIDS defining illness
- become pregnant

At enrolment women in each of the three study populations will be assigned randomly to one of the two following antiretroviral regimens

Intervention Arm:	Tenofovir, Lamivudine and Efavirenz (TDF/3TC/EFV)
Control arm:	Zidovudine, Lamivudine and Efavirenz (ZDV/3TC/EFV)

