## 9. Statistical Considerations

### 9.1 Sample Size:

The total number of women with HIV infection in the CAPRISA 004 and CAPRISA 008 studies is anticipated to be approximately 120 in the tenofovir gel exposed group. In addition 60 participants seroconverted in the 004 study on the placebo treatment arm.

If 50% of these participants need to be initiated on ART within the next 3 years, we would be able to randomise approximately 60 participants who were exposed to tenofovir gel to ART assignment. We also anticipate that 30 participants who seroconverted on the placebo arm will be eligible for randomisation to treatment assignment in the next 3 years (Table 1).

There are 3 study populations:

*Study population 1:* HIV positive women from the CAPRISA 004 tenofovir gel arm and HIV positive women from the clinical trial tenofovir gel provision arm of CAPRISA 008

*Study population 2:* HIV positive women in the placebo arm of CAPRISA 004

*Study population 3:* HIV positive women from the family planning service arm of CAPRISA 008

Participants will be randomised in each of the tenofovir gel exposed groups and the placebo gel exposed groups to either a tenofovir containing antiretroviral regimen or a tenofovir-sparing antiretroviral regimen.

The primary treatment outcome, treatment failure (treatment failure includes viral load > 50 copies/mL at 12 months, regimen changes for treatment failure within the first 12 months or death within the first 12 months), will be analysed in four different comparisons.

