#### Power

Comparison A: We anticipate that there will be 30 and 30 participants in the two arms.

Comparison B: We anticipate that there will be 20 and 10 participants in the two arms.

Comparison C: We anticipate that there will be 30 and 15 participants in the two arms.

Comparison D: We anticipate that there will be 30 and 15 participants in the two arms.

Power for Comparison A:

A Fisher's exact test with a 0.05 two-sided significance level will have 70% power to detect the difference between a Group 1 proportion, of 0.9 and a Group 2 proportion, of 0.6 when the sample size in the two groups is 30.

Power for Comparison B:

A Fisher's exact test with a 0.05 two-sided significance level will have 25% power to detect the difference between a Group 1 proportion, of 0.9 and a Group 2 proportion, of 0.6 when the sample sizes are 10 and 20, respectively.

Power for Comparison C and D:

A Fisher's exact test with a 0.05 two-sided significance level will have 43% power to detect the difference between a Group 1 proportion, of 0.9 and a Group 2 proportion, of 0.6 when the sample sizes in the two groups are 15 and 30 respectively.

**Table 1:** Statistical power estimates for comparison A based on a range of sample sizes and potential treatment failure rates

Sample size	Proportion with treatment failure			
	0.10 vs 0.30	0.10 vs 0.40	0.05 vs 0.40	0.10 vs 0.50
40/30	44	77	93	94
30/30	37	70	89	91
30/25	34	64	86	86
30/20	28	57	79	82
40/15	28	55	77	79
30/15	22	47	68	72
30/10	15	34	53	56
20/15	18	41	59	67

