**9.3 Data analysis plan**

A Statistical Analysis Plan (SAP) will outline the statistical analyses. The following is a summary of the planned analyses. Any deviations to be made from this summary plan will be documented in the detailed SAP.

A Fisher's exact test will be used to compare the proportion of participants with treatment failure in each of the two arms. We will also do a stratified Mantel Haenszel test where the stratum is the study arm a participant who seroconverted while randomised to tenofovir was in (004, 008 CAPRISA arm or 008 family planning arm). Placebo arm patients will not be stratified.

In addition, treatment failure at 24 and 36 months will be compared between the treatment arms using the same statistical methods as for the primary comparison at 12 months.

All primary analyses will be performed on an intention-to-treat (ITT) basis with additional analyses performed on the per protocol and as treated populations. For the ITT analysis, participants will be analysed according to the study arm, even if the participant did not follow the assigned procedures. The only participants excluded from this primary analysis population will be women with no post-randomisation visit and no data collected. All primary and secondary analyses will be two-sided and will be performed at the 0.05 level of significance.

The analyses of secondary objectives will be described in detail in the SAP.

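### Comparison A alone cannot separate a gel effect from a regimen difference, and the plan never formally combines C with D or uses the randomised regimen contrast in unexposed women

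*Protocol*

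**What the plan says.** Protocol 2.1 states what the trial mainly sets out to do: "To determine whether prophylactic exposure to tenofovir gel at the time of infection alters the subsequent therapeutic response to a tenofovir containing antiretroviral regimen". Section 7 randomises every population, including the placebo women of population 2: "At enrolment women in each of the three study populations will be assigned randomly to one of the two following antiretroviral regimens". Section 9.2 makes this 1:1, stratified by study population.

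Section 9.1 says that the primary outcome, treatment failure by 12 months, "will be analysed in four different comparisons":

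- **A**: tenofovir-containing against tenofovir-sparing regimen in exposed women. "This includes study population 1 and 3, i.e. only women who were in the tenofovir gel arm of a trial".
- **B**: population 1 against population 3, tenofovir regimen only.
- **C**: exposed (populations 1 and 3) against unexposed (population 2), tenofovir regimen only.
- **D**: exposed against unexposed, tenofovir-sparing regimen only.

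None of the four compares the regimens within population 2, and none tests regimen by exposure. Section 9.3 adds a Mantel-Haenszel test stratified by the exposed women's source arm, and says: "All primary and secondary analyses will be two-sided and will be performed at the 0.05 level of significance". Stated power is 70% for A, 25% for B, and 43% for each of C and D.

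**The concern.** The objective is about exposure; Comparison A is about regimen. If tenofovir and zidovudine regimens have different failure rates for reasons unrelated to the gel, A picks up that difference. A can then be significant with no gel effect, or close to null when the gel has worsened the response to tenofovir.

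Comparison C asks the right question, but its groups are not formed by randomisation at ART start. The exposed women come from two parent trials (CAPRISA 004 and 008), and the unexposed women only from the CAPRISA 004 placebo arm (section 5). A cohort difference unrelated to tenofovir would enter C. D can reveal such a difference, but C and D are each tested at 0.05 and then left side by side. A significant C with a non-significant D is not a test that the two differ. The trial could therefore report a regimen-specific gel effect, or miss one, on a pattern of p-values that does not bear on it.

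**Working it through.** **Inputs from Protocol 9.1.** Comparison A: "Comparison A: We anticipate that there will be 30 and 30 participants in the two arms". C and D have 30 exposed and 15 unexposed women each. The four cells are therefore 30 exposed-tenofovir, 30 exposed-zidovudine, 15 unexposed-tenofovir and 15 unexposed-zidovudine. The design rates are given as a "Group 1 proportion, of 0.9 and a Group 2 proportion, of 0.6 when the sample size in the two groups is 30". Table 1 shows the same case as failure of 0.10 against 0.40.

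**Reproducing the plan's power.** I used full enumeration of two binomials and Fisher's exact test, with the two-sided p as twice the smaller one-sided p.

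| Comparison | Stated | Recomputed |
|---|---|---|
| A (30/30) | 70% | 70.5% |
| B (10/20) | 25% | 25.4% |
| C, D (15/30) | 43% | 43.5% |

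The stated figures hold.

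**What A estimates.** Let F be the failure proportion.

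A = F(exposed, TDF) − F(exposed, ZDV)

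This equals the gel effect specific to tenofovir plus the TDF−ZDV difference that would exist without gel. The protocol gives no regimen-specific failure rates for unexposed women, so the rates below are assumptions. Exact Fisher, 30 against 30:

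| Scenario | TDF, exposed | ZDV, exposed | P(A significant) |
|---|---|---|---|
| No gel effect, regimens differ | 0.10 | 0.20 | 10% |
| No gel effect, regimens differ | 0.10 | 0.25 | 21% |
| No gel effect, regimens differ | 0.10 | 0.30 | 37% |
| No gel effect, regimens differ | 0.10 | 0.40 | 70.5% |
| Gel raises TDF failure from 0.10 to 0.30, ZDV at 0.30 | 0.30 | 0.30 | 2.6% |

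**What reading C beside D can do.** Suppose exposed women fail at 0.40 and unexposed at 0.10 on both regimens, so there is no regimen-specific gel effect. C and D use different women, so P(C significant and D not) = 0.435 × (1 − 0.435) = 0.435 × 0.565 ≈ 0.25. About one trial in four would show the misleading pattern.

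**The missing contrast.**

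DD = [F(exp, TDF) − F(exp, ZDV)] − [F(unexp, TDF) − F(unexp, ZDV)]

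Rearranged, DD = [F(exp, TDF) − F(unexp, TDF)] − [F(exp, ZDV) − F(unexp, ZDV)] = C − D.

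On the risk-difference scale it removes a regimen difference common to both exposure groups, and a cohort difference common to both regimens. In simulation (400,000 trials) with no gel effect and a regimen gap of 0.40 against 0.10 or 0.30 against 0.10, a Wald test of DD rejected in about 5% of trials.

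**Its precision.** Assume failure of 0.40 in exposed-tenofovir and 0.10 in the other three cells:

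- SE = √(0.24/30 + 0.09/30 + 0.09/15 + 0.09/15) = √0.023 = 0.152
- 95% half-width = 1.96 × 0.152 ≈ 0.30
- Power = Φ(0.30/0.152 − 1.96) ≈ 51% (49% simulated; about 20% on the logit scale)

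Comparison C by the same normal approximation:

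- SE = √(0.24/30 + 0.09/15) = √0.014 = 0.118
- Power = Φ(0.30/0.118 − 1.96) ≈ 72%

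In the masking scenario (last row of the table above, with unexposed women at 0.10 on TDF and 0.30 on ZDV), DD = 0.20 and SE = √(0.21/30 + 0.21/30 + 0.09/15 + 0.21/15) = √0.034 = 0.184, so power is about 19%. C by the same approximation has SE = √(0.21/30 + 0.09/15) = 0.114 and power of about 42%.

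**The case against.** The best defence is that the objective already has its own comparison. C sets exposed against unexposed women on the tenofovir regimen, D is a sensible negative control, and section 3.1 announces the exposed-unexposed comparison. A's stated hypothesis is only a regimen difference among exposed women. For that question it is a valid randomised answer, and the protocol nowhere says that a difference in A will be attributed to the gel. All of this stands. A reader might infer that the plan cannot address its objective at all, or that it misuses A; the documents support neither.

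A reader might also set the 51% for the new contrast beside the 43% stated for C and conclude that it costs no power. That mixes a normal approximation with a conservative exact test. Like for like it is 51% against 72%, and in the masking scenario C again does better.

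The regimen gaps used above are assumptions, and at 10% against 20% A rejects in only about 10% of trials. Section 9.3 is a summary, and an SAP not seen here could add an interaction estimate.

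What survives is narrower. The four comparisons of the primary outcome are fixed in the protocol, A is the best powered and the only one with a power table, C and D are not randomised contrasts, and nothing formally joins them.

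**Conclusion.** The point holds in a limited form. Comparison A cannot by itself answer the primary objective, because any intrinsic regimen difference is added to the gel effect. C does target the objective, but it is open to cohort differences, and comparing its significance with that of D does not test a regimen-specific effect. The randomised regimen contrast in population 2, which would help to separate these effects, appears in none of the four comparisons.

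The size depends on assumed rates: A is significant with no gel effect in 10% to 37% of trials for regimen gaps of 10 to 20 points, and in 2.6% when an equal regimen gap hides a 20-point gel effect. The structural problem needs only a non-zero regimen difference. The difference of differences corrects what is estimated; it does not rescue the power. Its cancellation is exact only on the additive scale, and its power for a 30-point effect is about 51% by normal approximation and about 20% on the logit scale. That is too low to make attribution to the gel conditional on it.

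**What to change.** In sections 9.1 and 9.3:

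1. Add the regimen-by-exposure difference of differences: tenofovir minus zidovudine failure in populations 1 and 3, minus the same in population 2. Note that it equals C minus D. Report it as an unstratified risk difference with a 95% CI; cells of 15 women are too small to split by site.
2. State that Comparison A alone will be read as a comparison of regimens in exposed women, not as evidence of a gel effect.
3. State that the new contrast is an estimate to be read with its interval and alongside C and D, not a decisive test.

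The cost is wording and a small amount of analysis. All four cells are already randomised and followed, so no extra women or visits are needed. The drawback is a wide interval, about 30 points either side under the assumed rates, which the report must show plainly.

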#### Comparison B:

Hypothesis: In women on tenofovir antiretroviral treatment, longer intervals for HIV testing while on tenofovir gel, lead to different treatment failure rates.

This comparison includes women in the tenofovir containing antiretroviral treatment arms of study populations 1 and 3. Treatment failure rates in the tenofovir containing antiretroviral treatment arm of study population 1 will be compared to the treatment failure rates in the tenofovir containing antiretroviral arm of study population 3.

#### Comparison C:

Hypothesis: Prior exposure to tenofovir gel leads to different treatment failure rates.

This comparison involves the tenofovir containing antiretroviral treatment arms of all three study populations. The treatment failure rate in the tenofovir containing antiretroviral treatment arm of study populations 1 and 3 will be compared to the treatment failure rate in the tenofovir containing antiretroviral treatment arm in study population 2.

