### 5. Study Population:

Women who become infected with HIV while participating in the CAPRISA 004 and CAPRISA 008 trials.

There are 3 study populations:

- Study population 1:* HIV positive women from the CAPRISA 004 tenofovir gel arm and HIV positive women from the clinical trial tenofovir gel provision arm of CAPRISA 008
- Study population 2:* HIV positive women in the placebo arm of CAPRISA 004
- Study population 3:* HIV positive women from the family planning service arm of CAPRISA 008

Women in any of the three study populations who become pregnant during follow-up will be initiated on their assigned treatment regimen, as appropriate, for prevention of mother-to-child transmission of HIV.

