### **5.3 Recruitment:**

Participants who have seroconverted while enrolled in the CAPRISA 004 study or the CAPRISA 008 study will be recruited for study participation. Participants who acquired HIV infection while in follow-up in the CAPRISA 004 study are currently in follow up in the CAPRISA 002 study (Viral Set Point and Clinical Disease Progression in HIV-1 subtype C infection: the role of immunological genetic and viral factors over the course of disease and during antiretroviral therapy, acute and early infection). All participants who become infected with HIV while in the CAPRISA 008 study will be referred to the CAPRISA 002 study for follow-up. When participants in CAPRISA 002 become eligible for antiretroviral therapy, they will be referred to this study for screening and enrolment.

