#### Comparison D:

Hypothesis: Prior exposure to tenofovir gel has no influence on treatment failure rates when a tenofovir-sparing regimen is used.

This comparison involves study populations 1, 2 and 3. The treatment failure rate in the tenofovir-sparing antiretroviral arm of study populations 1 and 3 will be compared to the treatment failure rate in the tenofovir-sparing antiretroviral treatment arm in study population 2.

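### Comparisons C and D set gel-exposed women from two trials against unexposed women from only one, so a difference between the trials cannot be separated from an effect of gel

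*Protocol*

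**What the plan says.** Section 5 of the Protocol defines three populations. Population 1 is "HIV positive women from the CAPRISA 004 tenofovir gel arm and HIV positive women from the clinical trial tenofovir gel provision arm of CAPRISA 008". Population 2 is "HIV positive women in the placebo arm of CAPRISA 004". Population 3 comes wholly from the family planning arm of CAPRISA 008. Under Comparison A, Section 9.1 describes everyone in populations 1 and 3 as having been on tenofovir gel when infected. The only unexposed women are therefore those from the 004 placebo arm.

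Comparison C states the hypothesis "Prior exposure to tenofovir gel leads to different treatment failure rates". For the groups it says: "The treatment failure rate in the tenofovir containing antiretroviral treatment arm of study populations 1 and 3 will be compared to the treatment failure rate". The comparator is population 2 on the same regimen. Comparison D repeats the structure on the other regimen: the pooled rate "will be compared to the treatment failure rate in the tenofovir-sparing antiretroviral treatment arm in study population 2".

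Section 9.3 names two analyses. The first is a Fisher's exact test on the two proportions. The second is a Mantel-Haenszel test whose strata are the source arms of the gel-exposed women (004, 008 CAPRISA arm, 008 family planning arm). It adds: "Placebo arm patients will not be stratified".

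Sections 7 and 9.2 randomise the ART regimen within each population. This trial does not randomise gel exposure.

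**The concern.** The primary objective (Section 2.1) asks whether gel exposure at the time of infection changes the response to a tenofovir-containing regimen. Comparison A contains only exposed women, so C is the comparison that addresses this question most directly. Section 9.1 lists C and D among the four comparisons of the primary outcome.

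The exposed and unexposed groups differ in more than gel. Some of the exposed women come from a different trial, and the unexposed women do not. Calendar time probably differs as well: Section 5.3 says that the 004 seroconverters are already in follow-up, whereas for the other trial it says "All participants who become infected with HIV while in the CAPRISA 008 study will be referred to the CAPRISA 002 study for follow-up". If women from the two source trials fail treatment at different rates for any reason, the pooled contrast would show that gap as a gel effect. It could equally hide a real gel effect. Neither of the two analyses that the Protocol names would reveal which had happened.

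**Working it through.** **1. Inputs.** Section 9.1 expects 30 exposed and 15 unexposed women in C, and the same in D. Comparison B splits the 30 exposed women on tenofovir into 20 from population 1 and 10 from population 3. The Study Schema gives 40, 30 and 20 women in populations 1, 2 and 3. Failure rates of 0.10 and 0.40 are a pair from Table 1.

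**2. The plan's own figure.** Section 9.1 states 43% power for C and D (0.9 against 0.6, n = 15 and 30, Fisher, two-sided 0.05). Exact enumeration over the two binomials gives 43.5% when each one-sided p-value is compared with 0.025. It gives 52.3% when the two-sided p-value is formed by summing probabilities. The first convention reproduces the stated figure. Both are shown below.

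**3. Can the stratified test help?** In the Mantel-Haenszel risk difference or odds ratio, a stratum counts only if it holds both groups. For the risk difference its weight is n1·n0/(n1 + n0), with n1 exposed and n0 unexposed women. In both 008 strata n0 = 0, so the weight is 0. Placebo women are not assigned to a stratum at all. If they were placed with 004, the test would reduce to 004 gel against 004 placebo, which the Protocol does not plan. The test is usable for Comparison A, where both regimens occur in every stratum.

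**4. How many exposed women come from 008?** Population 3 alone gives 20/2 = 10 of 30 per regimen, which is the minimum. Population 1 adds an unstated number. If the two 008 arms contribute equally (20 each), 40 of 60 exposed women are from 008, or 20 of 30 per regimen. A rough cross-check uses the 60 placebo infections and the anticipated 120 exposed infections (Section 9.1) and the 39% reduction in 004 (Section 1), and assumes similar follow-up in the two 004 arms. 004 gel infections are about 60 × 0.61 = 36.6. That is 36.6/120 = 0.305 of the exposed, leaving about 0.695 × 30 = 21 of 30 from 008. This share remains an assumption.

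**5. Size of the false difference with no gel effect.** If m of the 30 exposed women come from 008, the expected false difference is (m/30) × (p008 − p004). The chance of rejection comes from exact enumeration, with exposed failures Bin(30 − m, p004) + Bin(m, p008) and unexposed failures Bin(15, p004), taking p004 = 0.10.

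| m of 30 from 008 | p008 | False difference | Rejects, each tail 0.025 | Rejects, summed probabilities |
|---|---|---|---|---|
| any | 0.10 | 0 | 0.5% | 2.1% |
| 10 | 0.30 | 10/30 × 0.20 = 6.7 points | 1.0% | 2.7% |
| 10 | 0.40 | 10/30 × 0.30 = 10 points | 2.6% | 5.4% |
| 20 | 0.20 | 20/30 × 0.10 = 6.7 points | 1.2% | 2.9% |
| 20 | 0.30 | 20/30 × 0.20 = 13.3 points | 6.1% | 10.6% |
| 20 | 0.40 | 20/30 × 0.30 = 20 points | 17.2% | 24.9% |

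**6. Price of a 004-only contrast.** With an assumed 10 exposed women against 15 placebo women per regimen, and each tail at 0.025, power for 0.10 against 0.40 is 17.5% if the exposed women have the lower rate and 30.5% if they have the higher.

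**The case against.** The strongest defence has four parts.

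- **Deferral to the SAP.** Section 9.3 calls itself a summary, and an SAP that is not at hand may add adjustment or a 004-only analysis. This stands in part: one cannot infer that no adjustment is planned anywhere. But the Protocol itself fixes the comparison groups and the two tests, and those are what tie trial to exposure.
- **Priority.** Section 3.1 puts the randomised regimen comparison among exposed women first and presents exposed against unexposed as additional. That is fair, but Section 9.1 still gives all four comparisons the primary outcome, and A cannot answer a question about exposure.
- **No documented gap.** Women from both trials enter at the same two clinics, through the same follow-up cohort, under the same ART criteria, regimens and visits. This stands. Under the convention that matches the stated power, rejection passes 5% in the table only when 008 women fail at least three times as often as 004 women and 20 of 30 come from 008. A reader might infer serious false-positive inflation; the documents do not show it.
- **Wording.** The causal verb belongs to a hypothesis, not to a reported conclusion. That is true, but the Protocol does not say that the result is to be read more cautiously.

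Three stronger readings are tempting and not supported. First, 004 gel against 004 placebo is not a randomised-exposure analysis. It is limited to women who became infected, which gel itself made less likely, and then to those who reached ART eligibility and enrolled. Second, one might infer that 008 women must have needed ART sooner after infection to enter in the same window. The Protocol gives no 008 accrual dates, and pregnancy is also an ART trigger, so this is only a possibility. Third, adjusting for enrolment viral load and CD4 count would not cure the problem. Neither is source trial or calendar time, and both are measured after exposure.

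**Conclusion.** The concern holds as a matter of design. C and D are observational contrasts across trials, and source trial is inseparable from exposure in them except within 004. The estimate is shifted by (share of exposed women from 008) × (difference in failure rate between the trials). The share is at least about one third and, on the assumption of equal 008 arms, about two thirds. The second factor is unknown. With the illustrative rates of 0.10 and 0.40 the shift is 10 to 20 points. The effect on the false-positive rate may be modest: 2.6% to 17.2% over that range under the convention that matches the Protocol's power, or 5.4% to 24.9% under the other. The shift in the estimate is the main issue, because it is present whenever the trials differ, whether or not the test rejects. Comparison A is not affected.

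**What to change.** For both C and D:

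1. Report 004 gel against 004 placebo beside the pooled contrast, as the within-trial comparison free of the source-trial difference. State that it is still conditional on infection and ART eligibility, and so is not a fully randomised comparison.
2. State that the pooled C and D results will be interpreted as associations with prior gel exposure.
3. If an estimate adjusted for enrolment viral load and CD4 count is wanted, use exact or Firth logistic regression because failures will be few, and label it supportive only. Secondary objective 1 (Section 2.2) asks whether gel alters CD4 decline, so these covariates may lie on the pathway under study.

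The cost is some wording and a small amount of extra analysis, with no change to conduct or sample size. The downside is precision: the 004-only contrast may have only about 10 against 15 women per regimen (an assumption), so its interval will be wide and it should be read for direction and range rather than for significance.
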